MRD: Minimal residual disease testing will be performed in subjects who achieve complete response. MRD testing may be performed either by flow cytometry or PCR, whichever is more readily available at the study institution.

Subjects will continue their randomized treatment assignment until disease progression or unacceptable toxicity (whichever occurs first). In case toxicity precludes dosing of one agent (i.e dexamethasone, clarithromycin, lenalidomide), treatment regimen will continue with the remaining agents. Subjects unable to receive ALL the components of the assigned treatment arms will be removed from study after reasonable attempts to dose reduce and manage side effects. Subjects with elevations of AST/ALT greater than three times the upper limit of normal, with concomitant elevation of bilirubin 2 times the upper limit of normal, not attributable to disease, should be discontinued from treatment. Subjects can also be removed from study at investigator's discretion, or if they withdraw consent. At completion or early discontinuation of treatment, subjects will be followed for 30 additional days or up to the initiation of subsequent treatment (whichever occurs first), after which they will be off the active treatment phase of the study. Long term follow up for disease status and survival will proceed until the subject has withdrawn consent, is lost to follow up, or has died.

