9.5 Instruction for initiation of a new cycle

A new course of treatment may begin on the scheduled Day 1 of a new cycle if:

- Absolute neutrophil count (ANC) ≥ 750 cells/mm³
- Platelets count $\geq 50,000$ /mm³
- Any other drug-related adverse events that may have occurred have resolved to \leq grade 2 severity.

If these conditions are not met on Day 1 of a new cycle, the subject will be evaluated weekly and a new cycle of treatment will not be initiated until the toxicity has resolved as described above. If the toxicity does not resolve within four weeks, the patient will be taken off the study. If the dosing of clarithromycin, lenalidomide or dexamethasone was halted during the previous cycle and was restarted with a one-level dose reduction without requiring an interruption for the remainder of the cycle, then that reduced dose will be initiated on Day 1 of the new cycle. If the dosing of clarithromycin, lenalidomide or dexamethasone was omitted for the remainder of the previous cycle or if the new cycle is delayed due to toxicity newly encountered on the scheduled Day 1, then the new cycle will be started with dose modifications as described in Section 9.6 and Table 2.

If the start of a new cycle is delayed more than 4 weeks, the patient will be removed from the protocol.

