9.6 Dose Modification

Doses of study medications will be modified for toxicity as listed below in Tables 1, 2a, and 2b. Doses must be adjusted for adverse events deemed related to study drug by the investigator. Doses may be adjusted for adverse events related to study medications not listed below at the discretion of the investigator.

Unless otherwise noted, other drugs in the regimen should be continued when the dosing of one or more drugs is delayed due to toxicity.

During BiRd therapy, if toxicity occurs that would indicate an interruption in treatment, the toxicity should be attributed to one or more drugs in the BiRD regimen and dose modifications instituted as instructed in the “Action” column of the table below based on attribution. During maintenance therapy, if toxicity occurs that would indicate a lenalidomide dose modification, toxicity should be attributed to lenalidomide and dose modifications instituted as instructed in the “Action” column of the table below based on attribution.

Table 1: Dose Reduction Steps:

Lenalidomide Dose Reduction

Starting Dose	Lenalidomide PO 25mg/day on days 1-21 of a 28 day cycle
Dose Level -1	Lenalidomide PO 15mg/day on days 1-21 of a 28 day cycle
Dose Level -2	Lenalidomide PO 10 mg/day on days 1-21 of a 28 day cycle
Dose Level -3	Lenalidomide PO 5 mg/day on days 1-21 of a 28 day cycle
Dose Level -4	Lenalidomide PO 5 mg every other day for on days 1-21 of a 28 day cycle

Dexamethasone Dose Reduction

Starting Dose	40 mg PO on days 1, 8, 15 and 22 of a 28 day cycle
Dose Level -1	20 mg PO on days 1, 8, 15 and 22 of a 28 day cycle
Dose Level -2	8 mg PO on days 1, 8, 15 and 22 of a 28 day cycle
Dose Level -3	8 mg PO on days 1 and 15 of a 28 day cycle
Dose Level -4	4 mg PO on days 1 and 15 of a 28 day cycle

Clarithromycin Dose Reduction

Starting Dose	500 mg BID PO days 1-28 of a 28 day cycle
Dose Level -1	250 mg BID PO days 1-28 of a 28 day cycle

Dose Level -2	250 mg PO daily on days 1-28 of a 28 day cycle
Dose Level -3	250 mg PO daily on days odd days of a 28 day cycle
Dose Level -4	Discontinue drug

Table 2a: RD Dose Modification Instructions

Toxicity	NCI Toxicity Grade	Action

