Allergic reaction or hypersensitivity	\geq Grade 3	
 • Discontinue lenalidomide and take patient off study
Venous thrombosis/embolism	\geq Grade 3	
 • Hold (interrupt) lenalidomide and Start anticoagulation; restart lenalidomide at investigator's discretion (maintain dose level).
Gastritis, gastric or duodenal ulcer	\geq Grade 3	
 • Hold (interrupt) dexamethasone until \leq grade 1 • Reduce dexamethasone by 1 dose level and restart

Toxicity	NCI Toxicity Grade	Action
Edema	≥ Grade 3	
 • Reduce dexamethasone by 1 dose level • Use diuretics as needed
Confusion or mood alternations	≥ Grade 2	
 • Hold (interrupt) dexamethasone until ≤ grade 1 • Reduce dexamethasone by 1 dose level and restart
Muscle weakness	≥ Grade 3	
 • Reduce dexamethasone by 1 dose level • If symptoms persist continue to reduce dexamethasone by 1 dose level as needed.
Hyperglycemia	≥ Grade 3	
 • Reduce dexamethasone by 1 dose level • Treat with insulin or oral hypoglycemics as needed
Acute pancreatitis	≥ Grade 3	
 • Discontinue dexamethasone and patient off study.
Other non-hematologic toxicity assessed as treatment-related	≥ Grade 3	
 • Attribute toxicity to one or more drugs. Hold drug(s) attributed to toxicity for remainder of cycle. Reduce drug(s) attributed to toxicity by 1 dose level.*

Table 2b: BiRD Dose Modification Instructions

Toxicity	NCI Toxicity Grade	Action
Neutropenia	≥ Grade 3 with fever (temperature ≥ 38.5° C)	
 • Hold (interrupt) lenalidomide. • Follow CBC weekly. • If neutropenia has resolved to ≤ grade 2 prior to Day 21, restart lenalidomide at next lower dose level and continue through Day 21. If neutropenia is the only toxicity for which a dose reduction is required, G-CSF may be used and the lenalidomide dose maintained.

Toxicity	NCI Toxicity Grade	Action

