Diarrhea	≥ Grade 3	
 • Hold (interrupt) clarithromycin until ≤ grade 1, then reduce dose to 250 mg twice daily
Dyspepsia	≥ Grade 3	
 • Hold (interrupt) clarithromycin and dexamethasone dosing until ≤ grade 1 • Reduce dexamethasone OR clarithromycin by 1 dose level based on attribution and restart dexamethasone and clarithromycin
Anaphylaxis or Hepatic failure	≥ Grade 3	
 • Discontinue clarithromycin and patient is off study
Loss of appetite or Nausea	≥ Grade 3	
 • Hold (interrupt) clarithromycin until ≤ grade 1, then reduce dose to 250 mg twice daily
Gastritis, gastric or duodenal ulcer	≥ Grade 3	
 • Hold (interrupt) dexamethasone until ≤ grade 1 • Reduce dexamethasone by 1 dose level and restart
Edema	≥ Grade 3	
 • Reduce dexamethasone by 1 dose level • Use diuretics as needed
Confusion or mood alternations	≥ Grade 2	
 • Hold (interrupt) dexamethasone until ≤ grade 1 • Reduce dexamethasone by 1 dose level and restart
Muscle weakness	≥ Grade 3	
 • Reduce dexamethasone by 1 dose level • If symptoms persist continue to reduce dexamethasone by 1 dose level as needed.

Toxicity	NCI Toxicity Grade	Action
Hyperglycemia	≥ Grade 3	
 Reduce dexamethasone by 1 dose level Treat with insulin or oral hypoglycemics as needed
Acute pancreatitis	≥ Grade 3	
 Discontinue dexamethasone and patient off study.
Other non-hematologic toxicity assessed as treatment-related	≥ Grade 3	
 Attribute toxicity to one or more drugs. Hold drug(s) attributed to toxicity for remainder of cycle. Reduce drug(s) attributed to toxicity by 1 dose level.*

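### The liver stopping rule in section 4.1 is not carried into the dose-modification tables, whose residual row says hold and reduce for the same drug-related grade 3 or higher event

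*Combined protocol and SAP*

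**What the plan says.** Section 4.1 (Study Design) applies to both arms. Its trigger reads: "Subjects with elevations of AST/ALT greater than three times the upper limit of normal, with concomitant elevation of bilirubin 2 times the upper limit" (ULN in both cases). The sentence then gives the qualifier and the action together: "not attributable to disease, should be discontinued from treatment". It offers no hold, reduction or rechallenge. Earlier in the same paragraph it says that if toxicity rules out one agent, the regimen goes on with the others.

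Section 9.6 (Dose Modification) makes the tables the working instruction: "Doses of study medications will be modified for toxicity as listed below in Tables 1, 2a, and 2b". Both tables end with a residual row for "Other non-hematologic toxicity assessed as treatment-related" at grade 3 or higher. After attribution to one or more drugs, its action is: "Hold drug(s) attributed to toxicity for remainder of cycle. Reduce drug(s) attributed to toxicity by 1 dose level". For the rest of the regimen, section 9.6 adds: "Unless otherwise noted, other drugs in the regimen should be continued when the dosing of one or more drugs is delayed due to toxicity".

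Section 9.5 lists what must be true before a new cycle may begin. One item is "Any other drug-related adverse events that may have occurred have resolved to" grade 2 or lower, and a patient whose toxicity has not resolved within four weeks comes off study. If a drug was omitted for the remainder of the previous cycle, "then the new cycle will be started with dose modifications as described in Section 9.6 and Table 2".

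**The concern.** AST, ALT and bilirubin are measured weekly in cycle 1 and on day 1 of each later cycle (sections 10.2 and 10.3), so staff will see the trigger when it occurs and must act on it. Whoever makes the dosing decision will probably have the dose-modification tables open. For this event the tables show the less cautious action and give no sign that a stop exists elsewhere.

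The cross-references in section 9 do not lead back to section 4.1 either. Section 9.1 sends the reader to section 9.2 for other reasons to discontinue, but section 9.2 holds study-level termination rules. Section 9.4 points to section 9.3 for dose modifications, but section 9.3 is supportive care. Section 10.11, which lists the grounds for removing an individual patient, has general excessive-toxicity criteria and does not list the liver rule.

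What is at stake is re-exposure of a patient with a combined transaminase and bilirubin rise, the patient section 4.1 is written to protect.

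**Working it through.** No formula applies: the point uses no sample size, event count or significance level. The check follows one case through the texts and then counts table rows.

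**Case.** AST/ALT above 3 x ULN with bilirubin 2 x ULN, not attributable to disease, attributed to study drug, grade 3 or higher.

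| Place | Instruction for this patient |
|---|---|
| 4.1 | Discontinue treatment |
| Tables 2a and 2b, residual row | Hold the attributed drug(s) to the end of the cycle; reduce by one level |
| 9.6 | Continue the other drugs, unless otherwise noted |
| 9.5 | A new cycle may begin once the event is grade 2 or lower within four weeks; a drug omitted for the rest of the previous cycle resumes at the modified dose |
| 10.11 | Removal possible on judgement; liver criterion not listed |

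**Illustration.** Suppose a BiRd patient's event is attributed to clarithromycin at the starting dose. Under the tables, clarithromycin is held to the end of the cycle while lenalidomide and dexamethasone go on. Once the event is grade 2 or lower within four weeks, the next cycle may open with clarithromycin at 250 mg twice daily (Table 1, level -1). Under section 4.1 treatment ends. Reducing a drug by one level has meaning only if it is given again, so the two actions cannot both be followed.

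**Same trigger, grade 2 or lower.** No table row applies and section 9.5 does not bar the next cycle. Section 4.1 is then the only instruction on the point and nothing opposes it.

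**Row count, visible rows.**

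- Table 2a (Rd): 19 toxicity rows. Five take the patient off study: grade 4 or desquamating rash, erythema multiforme, arrhythmia of grade 3 or higher, allergic reaction of grade 3 or higher, and acute pancreatitis.
- Table 2b (BiRd): 23 toxicity rows. Six take the patient off study: the same five plus anaphylaxis or hepatic failure.
- Off-study rows in total: 5 + 6 = 11. Rows stating the section 4.1 criterion: 0.
- Rows naming a liver event: 0 in Table 2a and 1 in Table 2b, although section 4.1 covers both arms. A BiRd event recorded as hepatic failure of grade 3 or higher is already off study, so the mismatch concerns events not recorded in that way, and any such event in the Rd arm.

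**The case against.** The strongest reply is that no real contradiction exists. Section 4.1 gives an exact laboratory criterion with a definite action, while the competing row is a residual category; a named stop should prevail over a catch-all. The continuation sentence in section 9.6 carries its own exception, and section 4.1 can be read as that exception. That sentence also speaks of dosing that is delayed, not of treatment that has ended. The tables are not presented as the only source of stops: the four-week rule sits in sections 9.4 and 9.5, and section 10.11 has its own list. The treat-until-unacceptable-toxicity rule in section 4.1 and the judgement criteria in section 10.11 point the same way, and nothing tells an investigator to disregard section 4.1.

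Most of this stands. It settles how the protocol is best read, but it does not put the rule where dosing decisions are made, and the precedence has to be inferred.

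A reader might also infer that section 9.5 orders the patient back onto treatment. It does not. The section opens by saying when a new cycle may begin, and its sentence on starting with dose modifications sets the dose for a patient who is continuing. The tension comes from the hold-and-reduce action of the residual row, with section 9.5 permitting the next cycle.

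Finally, the residual row's action ends in an asterisk whose footnote does not appear in the available text. That footnote might bear on precedence, so the statement that nothing refers to section 4.1 is limited to what is visible.

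**Conclusion.** The point holds as a low-severity safety inconsistency. For a treatment-related event of grade 3 or higher that meets the section 4.1 criterion, the protocol prints two different actions. The more cautious one is best read as governing, but the dosing sections do not visibly point to it. A site working from the tables as written could re-treat a patient who should have stopped.

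The number of patients affected cannot be derived. The documents give no expected rate of such events and do not print the CTCAE cut-offs, so the split between the grade 3 or higher mismatch and the silence at lower grades is also unknown.

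Three stronger readings go too far:

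- That the protocol lacks a liver stop. It has one, in section 4.1, and it is in force.
- That the conflict extends to every event meeting the trigger. At grade 2 or lower the tables are only silent.
- That the inconsistency biases the comparison of arms, PFS or power. Nothing in the documents supports that.

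The conclusion assumes that the missing footnote does not already refer to section 4.1.

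**What to change.** Add the same row to Tables 2a and 2b: AST/ALT >3 x ULN with bilirubin at least 2 x ULN, not attributable to disease: discontinue all study drugs (section 4.1). Section 4.1 gives the bilirubin limit as a bare multiple, so the sponsor should confirm that at least 2 x ULN is meant.

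State in sections 9.5 and 9.6 that this row takes precedence over the residual non-hematologic row, the sentence on continuing other drugs, and the new-cycle rules. Follow-up for progression and survival continues as in section 4.1. A matching line in section 10.11 is optional; if added, it should be worded as stopping treatment, not as leaving follow-up.

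The cost is a protocol clarification: one row in each of two tables and a precedence sentence in each of two sections. The tests are already scheduled, and the sample size and analysis do not change.

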4.1.4 Disease Assessment

At the end of every cycle (which may coincide with day 1 of the new cycle), response and toxicity will be evaluated. During cycle 1, patients will have lab work done weekly (CBC with differential and blood electrolytes) and female of childbearing potential will have their pregnancy testing done on Day 1, (see Appendix III). All patients will remain on study until disease progression or side effects become excessive.

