2.2 Study Endpoints

- Progression free survival
- Response rate by IMWG criteria (see Appendix I)
- Event free survival (an event is defined by coming off protocol for any reason, including progression of disease, lack of disease response, regimen intolerance, or death).
- Overall survival
- Duration of response
- Time to progression
- Progression free survival 2: time from study entry until 2nd instance of disease progression

- Quality of life: as measured by Functional Assessment of Chronic Illness Therapy – Fatigue (FACIT-Fatigue) Scale (Appendix IX) as part of a quality of life assessment.
- Regimen toxicities, as defined by CTCAE V4.0

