14.4 Analysis of Secondary Endpoints

Secondary endpoints include objective response rate (CR+PR) and complete response rate (CR) (estimated via binomial proportions), and Kaplan-Meier overall survival. Overall survival will be defined as the time from randomization day until death. Ninety-five percent confidence intervals will be calculated for the objective response proportion in each group via binomial proportions. Comparison of the objective response rate and complete response rate between the treatment groups will be performed by the chi-square test. The comparison of the overall survival distributions between the treatment groups will be performed by the log-rank test. Analysis of these three secondary endpoints will

be considered hypothesis-generating only and will be adjusted for multiplicity of outcomes by the Bonferroni method. In the event that no significant result is observed for the primary endpoint (PFS), significant findings for the secondary endpoints (even after correction for multiplicity of outcomes) will not result in efficacy claims for labeling purposes. Similarly, if a significant finding is observed for the primary endpoint, significant findings for the secondary endpoints will still not result in efficacy claims for labeling purposes. All other secondary endpoints (i.e., event-free survival, duration of response, time to progression, progression-free survival 2, and quality of life measures) will only be descriptively presented for each treatment group and no formal statistical comparison will be made between treatment arms. Confidence intervals for the secondary endpoints of objective response rate, complete response rate, and overall survival will be Bonferroni-corrected. The frequency of subjects experiencing toxicities will be tabulated. Toxicities will be assessed and graded according to CTCAE v. 4.0 terminology. Exact 95% confidence intervals around the toxicity proportions will be calculated to assess the precision of the obtained estimates.

All p-values will be two-sided with statistical significance evaluated at the 0.05 alpha level. P-values will be Bonferroni-corrected for the secondary endpoints of objective response rate, complete response rate, and overall survival. All analyses will be performed in SAS Version 9.4 (SAS Institute, Inc. Cary, NC) and Stata Version 14.0 (StataCorp, College Station, TX).

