APPENDIX I: Criteria for Response

Table 1: Criteria for Response, Disease plateau, and Disease Relapse as adopted from the EBMT and the international uniform response criteria³⁵

Stringent Complete Response (sCR) requires all of the following:

  All of the criteria of complete response  Normal serum free light chain ratio  Absence of monoclonal cells on bone marrow aspirate by immunohistochemistry or immunofluorescence
Complete Response (CR) requires all of the following:

  Absence of the original monoclonal protein in serum and urine by immunofixation. The presence of oligoclonal bands consistent with oligoclonal immune reconstitution does not exclude CR.  ≤5% plasma in a bone marrow aspirate and also on trephine bone biopsy, if biopsy is performed. If absence of monoclonal protein is sustained for 6 weeks it is not necessary to repeat the bone marrow, except in patients with non-secretory myeloma where the marrow examination must be repeated after an interval of at least 6 weeks to confirm CR.  No increase in size or number of lytic bone lesions (development of a compression fracture does not exclude response)  Disappearance of soft tissue plasmacytoma.
Very Good Partial Response (VGPR) requires all of the following:

  Negative serum and urine protein electrophoresis with persistence of monoclonal protein detectable on immunofixation OR  ≤90% reduction in serum monoclonal protein level with urine monoclonal protein level < 100mg in 24 hour collection.
Partial Response (PR) requires all of the following:

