
  ≥50% reduction in the level of the serum monoclonal paraprotein.  Reduction in 24h urinary light chain excretion either by ≥90% or to <200mg.  For patients with light chain only disease, then a 50% reduction in the difference between the involved and unininvolved free light chain level may be substituted for the M-protein measurement.  For patients with non-secretory myeloma only, ≥50% reduction in plasma cells in a bone marrow aspirate and on trephine bone biopsy, if biopsy is performed.  ≥50% reduction in the size of soft tissue plasmacytomas (by radiography or clinical examination).  No increase in size or number of lytic bone lesion (development of a compression fracture does not exclude response)
Stable Disease (SD) requires the following:

  Not meeting the criteria stringent complete response (sCR), complete response (CR), very good partial response (VGPR), or partial response (PR)
Plateau:

  Stable values (within 25% above or below value at the time response is addressed) 
Patients in which no significant change (<50% decrease or <25% increase from baseline) in the production rate of the monoclonal serum protein or Bence-Jones protein excretion and no new lytic lesions and/or plasmacytomas are detected.

Relapse from CR requires at least one of the following:

- Reappearance of serum or urinary paraprotein on immunofixation or routine electrophoresis, confirmed by at least one further investigation and excluding oligoclonal immune reconstitution.
- ≥5% plasma in a bone marrow aspirate or trephine bone biopsy.
- Development of new lytic lesions of soft tissue plasmacytomas or definite increase in the size of residual bone lesions (development of a compression fracture does not exclude continued response and may not indicate progression).
- Development of hypercalcemia (corrected serum calcium >11.5mg/dl or 2.8 mmol/l) not attributable to any other cause.

Progressive disease (PD) for patients not in CR requires one or more of the following:

- >25 increase in the level of the serum monoclonal paraprotein, which must also be an absolute increase of at least 5g/L and confirmed by at least one repeated investigation.

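### Appendix I sets no repeat reading for PR or VGPR, so the tested ORR can count transient single-visit crossings as responses

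*Combined protocol and SAP*

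**What the plan says.** Section 4.1.4 has response scored each 28-day cycle: "At the end of every cycle (which may coincide with day 1 of the new cycle), response and toxicity will be evaluated". The Schedule of Assessments (1.3) and Section 10.3 put serum electrophoresis and immunofixation, free light chains and 24-hour urine on Day 1 of every cycle. Treatment continues until progression or unacceptable toxicity (4.1).

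Section 2.2 refers response rate to the IMWG criteria as set out in Appendix I. There, "Partial Response (PR) requires all of the following", and the serum item is "≥50% reduction in the level of the serum monoclonal paraprotein". The other items cover urine, light-chain-only disease, non-secretory disease, plasmacytomas and lytic lesions. None of the PR or VGPR items mentions a second reading.

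Progression is treated differently. The serum item needs a rise "which must also be an absolute increase of at least 5g/L and confirmed by at least one repeated investigation". The urine item has the same repeat condition, and reappearance of paraprotein after CR needs a further investigation. For CR there is a persistence clause, "If absence of monoclonal protein is sustained for 6 weeks it is not necessary to repeat the bone marrow", but it waives a second marrow and is not a rule for PR or VGPR.

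Section 14.4 defines ORR as CR+PR and states: "Comparison of the objective response rate and complete response rate between the treatment groups will be performed by the chi-square test". It makes ORR, CR rate and OS hypothesis-generating, Bonferroni-adjusted, and not a basis for labelling claims. It does not say whether ORR is best response at any visit or response at a fixed time. The phrase best response rate occurs only in the rationale (3.8).

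**The concern.** The appendix does not accept a single M-protein value as evidence of worsening, but accepts one as evidence of improvement. There is no absolute floor on the improvement side either. Entry is allowed just above 0.5 g/dL serum M-protein (5.1), so a fall of about 0.25 g/dL can meet the serum PR item, while serum progression needs a rise of at least 5 g/L, which is 0.5 g/dL.

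With a reading every month, a patient whose true fall stays short of 50% has many chances to cross the line once through measurement error. If ORR is best response, that one crossing decides the classification. The trial is open-label, and the only independent review mentioned (14.3) concerns radiological progression, not response.

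At stake are the level and interpretability of a formally tested secondary endpoint, and the start date for duration of response. A response rule settled after outcomes are known in an open-label trial would also be open to question.

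**Working it through.** **Is a rule supplied elsewhere?** Sections 4.1.4, 9.1, 10.3, 14.3 and 14.4 add no confirmation requirement for PR or VGPR. The confirmation notes in 1.3 and 10.3 concern marrow or imaging for CR, progression or clinical indication. The gap is real on the face of the documents.

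**The plan's own figure.** Section 14.2 states 133 PFS events for 90% power at a hazard ratio of 1.75. Schoenfeld: 4 × (1.960 + 1.282)² / (ln 1.75)² ≈ 134.2, rounded up to 135. The design reproduces closely and is unaffected by this point. No power or sample size is stated for ORR.

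**Direction for each arm.** Every confirmed response is also an unconfirmed one. Dropping confirmation can only add responders, so ORR is at least as high in each arm.

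**Size.** These inputs are assumptions, not document values:
- independent lognormal error on baseline and on each follow-up reading, CV 5%, 10% or 15%;
- 12 monthly readings;
- true falls of non-responders uniform on 0–50% and constant over visits;
- the serum item decisive.

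Share f of true non-responders scored PR, by simulation:

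| CV | any single reading | two consecutive readings |
|---|---|---|
| 5% | 9% | 4% |
| 10% | 19% | 9% |
| 15% | 30% | 14% |

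A patient with a true 40% fall at CV 10% is scored PR at some visit with probability 43%, against 14% under the two-reading rule.

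**Effect on the comparison.** Take 90.3% (BiRd) and 79.1% (Rd) from Section 3.8 as illustrative true rates. Observed ORR = p + (1 − p) × f. With the same f in both arms the difference is 11.2 × (1 − f) points. Power is for a two-proportion test with 153 per arm at 0.05/3; it is 63% with no error.

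- Single reading, f = 0.19: BiRd 90.3 + 9.7 × 0.19 = 92.1%; Rd 79.1 + 20.9 × 0.19 = 83.1%; difference 11.2 × 0.81 = 9.1 points; power about 51%.
- Two readings, f = 0.09: 91.2% v 81.0%; difference 10.2 points; power about 57%.

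**When f differs by arm.** The difference exceeds 11.2 points when 9.7 × f(BiRd) > 20.9 × f(Rd), that is, when f(BiRd)/f(Rd) > 20.9/9.7 = 2.15. Two plausible departures, both at CV 10%:

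- BiRd non-responders lie nearer the threshold (true falls 30–50%), Rd as before: f ≈ 0.46 v 0.19, ORR 94.7% v 83.1%, difference 11.7 points, power 81%.
- BiRd patients stay under observation longer (24 readings v 6): f ≈ 0.22 v 0.15, power about 62%, almost the error-free value.

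**The case against.** **The arm difference.** A reader might infer that the missing rule narrows the BiRd–Rd difference and costs power. The documents do not support that as a general statement. It needs similar false-responder rates in the two arms, and if BiRd works, longer observation alone pushes its rate up. The examples above show the difference widening in one case and power hardly changing in another. This objection stands.

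**One low value makes a responder.** This is also too strong. PR needs every applicable item, so a serum crossing may not suffice where urine, plasmacytoma or bone items apply. It also presumes best response, which 14.4 does not state. Nor does the asymmetry cover all progression: marrow, bone, plasmacytoma and hypercalcaemia items carry no repeat condition.

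**The magnitude.** The documents give no assay CV, no distribution for non-responders and no visit count. Holding each patient at the best true fall for 12 visits is generous to the concern; letting true change range from a 50% fall to a 25% rise cuts the CV 10% share from 19% to about 12%. The 79.1% and 90.3% come from a retrospective matched comparison and may already contain such error. The figures show scale only.

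**The cited criteria.** Whether the published criteria behind Appendix I carry a general confirmation rule cannot be checked from these documents. What can be said is that the appendix, as the operative text, is silent.

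**Consequence.** ORR is hypothesis-generating, duration of response is only described, and neither touches the primary analysis. That limits severity but does not remove the gap.

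**Conclusion.** The gap holds. Appendix I leaves PR and VGPR unconfirmed while requiring a repeat for serum and urine progression and for paraprotein relapse from CR, and nothing else in the plan fills it. If ORR is best response, it is inflated relative to a confirmed rule, and duration of response can be dated from a reading that does not persist.

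That direction follows from logic. The amount, roughly 9–30% of true non-responders under a single-reading rule against 4–14% under a two-reading rule, rests on an assumed CV of 5–15%, 12 readings and a uniform spread of true falls. No firm statement about the arm difference or power is warranted.

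This is a minor point, worth correcting because the correction is cheap.

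**What to change.** In Appendix I and Section 14.4, define ORR as best confirmed response. PR or VGPR counts when the serum, urine or free-light-chain criterion, as applicable, is met at two consecutive scheduled assessments, with response dated at the first; a deeper second reading also confirms. State in 14.4 that ORR is best response on study. Report unconfirmed ORR as a sensitivity analysis. Settle the rule before outcome data are reviewed. It should govern endpoint classification only.

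The cost is wording: the next cycle's tests are already in Schedule 1.3. Reported ORRs will be slightly lower, because patients who leave after one qualifying reading count as non-responders. Even with all 12 readings, two consecutive readings miss about 1–2% of true responders in the same error model (CV 5–15%, true falls assumed uniform on 50–100%).

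In the same edit, reconcile two adjacent wordings: VGPR is printed as "≤90% reduction in serum monoclonal protein level with urine monoclonal protein level < 100mg in 24 hour collection", where the inequality appears reversed, and 14.4 writes ORR as CR+PR without naming VGPR or sCR.
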